## 8. DEFINITION OF ANALYSIS POPULATIONS

The “Enrolled” population will consist of all participants randomly assigned to study intervention (mirikizumab).

The “Safety” population will consist of all participants randomly assigned to, and who received at least one single injection of study intervention (mirikizumab). Participants will be analyzed according the intervention they actually received.

The “Pharmacokinetic” population will consist of all enrolled participants who received a full dose of study intervention (mirikizumab) and have evaluable PK data.

All protocol deviations that occur during the study will be considered for their severity/impact and will be taken into consideration when participants are assigned to analysis populations.

## 9. STATISTICAL METHODOLOGY

### 9.1 General

Data listings will be provided for all data that is databased. Summary statistics and statistical analysis will only be presented for data where detailed in this SAP. For continuous data, summary statistics will include the arithmetic mean, arithmetic standard deviation (SD), median, minimum, maximum and n; for log-normal data (e.g. the PK parameters: AUCs and  $C_{max}$ ) the geometric mean and geometric (CV%) will also be presented. For categorical data, frequency count and percentages will be presented. Data listings will be provided for all participants up to the point of withdrawal, with any participants excluded from the relevant population highlighted. Summary statistics and statistical analyses will generally only be performed for participants included in the relevant analysis population. For the calculation of summary statistics and statistical analysis, unrounded data will be used.

Mean change from baseline is the mean of all individual participants' change from baseline values. Each individual change from baseline will be calculated by subtracting the individual participant's baseline value from the value at the timepoint. The individual participant's change from baseline values will be used to calculate the mean change from baseline using a SAS procedure such as Proc Univariate.

Data analysis will be performed using SAS® Version 9.4 or greater.

## 9.2 Demographics and Participant Disposition

Participant disposition will be summarized and listed. The demographic variables age, sex, race, ethnicity, country of enrolment, site ID, body weight, weight category, height and body mass index will be summarized by treatment and injection site, and listed. All other demographic variables will be listed only.

### 9.3 Pharmacokinetic Assessment

### 9.3.1 Pharmacokinetic Analysis

PK parameter estimates will be determined using non-compartmental procedures in validated software program (Phoenix WinNonlin Version 8.1 or later).

Serum concentrations of mirikizumab will be used to determine the following PK parameters, when possible:

Parameter	Units	Definition
AUC(0-t last )	day* $\mu\text{g}/\text{mL}$	area under the concentration versus time curve from time zero to time t, where t is the last time point with a measurable concentration
AUC(0-∞)	day* $\mu\text{g}/\text{mL}$	area under the concentration versus time curve from time zero to infinity
%AUC(t last -∞)	%	percentage of AUC(0-∞) extrapolated
C max	$\mu\text{g}/\text{mL}$	maximum observed drug concentration
t max	day	time of maximum observed drug concentration
t 1/2	day	half-life associated with the terminal rate constant ( $\lambda_z$ ) in non-compartmental analysis
CL/F	L/day	apparent total body clearance of drug calculated after extra-vascular administration
V z/F	L	apparent volume of distribution during the terminal phase after extra-vascular administration
V ss/F	L	apparent volume of distribution at steady state after extra-vascular administration

Additional PK parameters such as weight-normalized PK parameter estimates may be calculated, as appropriate. The software and version used for the final analyses will be specified in the CSR. Any exceptions or special handling of data will be clearly documented within the final CSR.

## Formatting of tables, figures and abbreviations **CC1**

### The version of the tool

effective at the time of PK analysis will be followed.

## General PK Parameter Rules

- Actual sampling times will be used in the final analyses of individual PK parameters, except for non-bolus predose sampling times which will be set to zero.
- $C_{max}$  and  $t_{max}$  will be reported from observed values. If  $C_{max}$  occurs at more than one time point,  $t_{max}$  will be assigned to the first occurrence of  $C_{max}$ .
- AUC parameters will be calculated using a combination of the linear and logarithmic trapezoidal methods (linear-log trapezoidal rule). The linear trapezoidal method will be applied up to  $t_{max}$  and then the logarithmic trapezoidal method will be used after  $t_{max}$ . The minimum requirement for the calculation of AUC will be the inclusion of at least three consecutive concentrations above the lower limit of quantification, with at least one of these concentrations following  $C_{max}$ .
- AUC( $0-\infty$ ) values where the percentage of the total area extrapolated is more than 20% will be flagged. Any AUC( $0-\infty$ ) value excluded from summary statistics will be noted in the footnote of the summary table.
- Half-life ( $t_{1/2}$ ) will be calculated, when appropriate, based on the apparent terminal log-linear portion of the concentration-time curve. The start of the terminal elimination phase for each subject will be defined by visual inspection and generally will be the first point at which there is no systematic deviation from the log-linear decline in serum concentrations. Half-life will only be calculated when a reliable estimate for this parameter can be obtained comprising of at least 3 data points. If  $t_{1/2}$  is estimated over a time window of less than 2 half-lives, the values will be flagged in the data listings. Any  $t_{1/2}$  value excluded from summary statistics will be documented in the footnote of the summary table.
- A uniform weighting scheme will be used in the regression analysis of the terminal log-linear portion of the concentration-time curve.
- The parameters based on observed last quantifiable drug concentration ( $C_{last}$ ) will be reported.

## Individual PK Parameter Rules

- Only quantifiable concentrations will be used to calculate PK parameters with the exception of special handling of certain concentrations reported below the lower limit of quantitation (BQL). Serum concentrations reported as BQL will be set to a value of zero when all of the following conditions are met:
  - The compound is non-endogenous.
  - The samples are from the initial dose period for a subject or from a subsequent dose period following a suitable wash-out period.

- The time points occur before the first quantifiable concentration.
- All other BQL concentrations that do not meet the above criteria will be set to missing.
- Also, where two or more consecutive concentrations are BQL towards the end of a profile, the profile will be deemed to have terminated and therefore any further quantifiable concentrations will be set to missing for the calculation of the PK parameters unless it is considered to be a true characteristic of the profile of the drug.

### **Individual Concentration vs. Time Profiles**

- Individual concentrations will be plotted utilizing actual sampling times.
- The terminal point selections will be indicated on a semi-logarithmic plot.

### **Average Concentration vs. Time Profiles**

- The average concentration profiles will be graphed using scheduled (nominal) sampling times.
- The average concentration profiles will be graphed using arithmetic average concentrations.
- The predose average concentration for single-dose data from non-endogenous compounds will be set to zero. Otherwise, only quantifiable concentrations will be used to calculate average concentrations.
- Concentrations at a sampling time exceeding the sampling time window specified in the protocol, or  $\pm 10\%$ , will be excluded from the average concentration profiles.
- Concentrations excluded from the mean calculation will be documented in the CSR.
- A concentration average will be plotted for a given sampling time only if 2/3 of the individual data at the time point have quantifiable measurements that are within the sampling time window specified in the protocol or  $\pm 10\%$ . An average concentration estimated with less than 2/3 but more than 3 data points may be displayed on the mean concentration plot if determined to be appropriate and will be documented within the final CSR.

### **Treatment of Outliers during Pharmacokinetic Analysis**

Application of this procedure to all PK analyses is not a requirement. Rather, this procedure provides justification for exclusion of data when scientifically appropriate. This procedure describes the methodology for identifying an individual value as an outlier for potential exclusion, but does not require that the value be excluded from analysis. The following methodology will not be used to exclude complete profiles from analysis.

### Data within an Individual Profile

A value within an individual profile may be excluded from analysis if any of the following criteria are met:

- For PK profiles during single dosing of non-endogenous compounds, the concentration in a predose sample is quantifiable.
- For any questionable datum that does not satisfy the above criteria, the profile will be evaluated and results reported with and without the suspected datum.

### Data between Individual Profiles

1. If  $n < 6$ , then the dataset is too small to conduct a reliable range test. Data will be analyzed with and without the atypical value, and both sets of results will be reported.
2. If  $n \geq 6$ , then an objective outlier test will be used to compare the atypical value to other values included in that calculation:
  - a. Transform all values in the calculation to the logarithmic domain.
  - b. Find the most extreme value from the arithmetic mean of the log transformed values and exclude that value from the dataset.
  - c. Calculate the lower and upper bounds of the range defined by the arithmetic mean  $\pm 3 \times \text{SD}$  of the remaining log-transformed values.
  - d. If the extreme value is within the range of arithmetic mean  $\pm 3 \times \text{SD}$ , then it is not an outlier and will be retained in the dataset.
  - e. If the extreme value is outside the range of arithmetic mean  $\pm 3 \times \text{SD}$ , then it is an outlier and will be excluded from analysis.

If the remaining dataset contains another atypical datum suspected to be an outlier and  $n \geq 6$  following the exclusion, then repeat step 2 above. This evaluation may be repeated as many times as necessary, excluding only one suspected outlier in each iteration, until all data remaining in the dataset fall within the range of arithmetic mean  $\pm 3 \times \text{SD}$  of the log-transformed values.

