### Reporting of Excluded Values

Individual values excluded as outliers will be documented in the final CSR. Approval of the final CSR will connote approval of the exclusion.

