#### **9.3.2 Pharmacokinetic Statistical Methodology**

The  $C_{\max}$ ,  $\text{AUC}(0-\infty)$ , and  $\text{AUC}(0-t_{\text{last}})$  will be log-transformed and analyzed using a linear fixed-effects model. The model will include delivery device, injection location, and weight

stratification as fixed-effects. The dosing regimen differences between the AI (Test) and PFS (Reference) administrations will be back-transformed to present the ratios of geometric least squares means and the corresponding 90% CI.

Example SAS Code:

```
proc mixed data=xxx;
by parameter;
class device location strat_weight;
model log_pk = device location strat_weight / residual;
lsmeans device / alpha=0.1 cl pdiff;
ods output lsmeans=lsmeans diffs=diffs;
run;
```

The  $t_{max}$  of mirikizumab between the AI (Test) and PFS (Reference) administrations will be analyzed using a Wilcoxon rank sum test. Estimates of the median difference, 90% CIs, and p-values from the Wilcoxon rank sum test will be calculated.

Additional comparisons will be made between:

- The 2 delivery devices (AI [Test] versus PFS [Reference]) separately at each injection location (injection location will be removed from the model above)
- The 3 injection locations (arm [Test] versus abdomen [Reference] and thigh [Test] versus abdomen [Reference]) separately for each device (device will be removed from the model above)

The 2 delivery devices (AI [Test] versus PFS [Reference]) will be considered bioequivalent if the 90% CIs of the ratio of geometric least squares means of  $C_{max}$ ,  $AUC(0-\infty)$ , and  $AUC(0-t_{last})$  fall within 0.8 to 1.25. CCI

Additional PK analyses may be conducted if deemed appropriate.

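### The SAP's ± 3 SD outlier rule allows Cmax and AUC values to be deleted without a cause, does not exempt the primary bioequivalence model, and promises no all-data result at the planned sample size

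*SAP*

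**What the plan says.** - **SAP 9.3.1, Treatment of Outliers during Pharmacokinetic Analysis.** The procedure is introduced as optional: "Application of this procedure to all PK analyses is not a requirement". It identifies candidate values "but does not require that the value be excluded from analysis". Exclusion is tied to scientific appropriateness, which is not defined. The method may not remove a complete profile.
- **SAP 9.3.1, Data between Individual Profiles, n < 6.** "Data will be analyzed with and without the atypical value, and both sets of results will be reported".
- **Same subsection, n ≥ 6.** The test is to "compare the atypical value to other values included in that calculation". Values are log-transformed, the most extreme is set aside, and mean ± 3 SD is formed from the rest. If the value falls outside, "then it is an outlier and will be excluded from analysis" (step 2e). The test may be repeated, one value per pass while n ≥ 6, until everything left is inside. The condition for repeating is: "If the remaining dataset contains another atypical datum suspected to be an outlier".
- **SAP 9.3.1, Data within an Individual Profile.** A questionable datum inside one profile is reported both ways.
- **SAP 9.3.1, Reporting of Excluded Values.** Exclusions are documented in the CSR, and "Approval of the final CSR will connote approval of the exclusion".
- **SAP 9.3.2.** The devices "will be considered bioequivalent if the 90% CIs of the ratio of geometric least squares means of" Cmax, AUC(0-∞) and AUC(0-tlast) lie within 0.8 to 1.25. This section neither invokes the outlier procedure nor shuts it out.
- **Protocol 9.2 and 9.3; SAP 8.** The PK population is defined by a full dose and evaluable data. Protocol 9.3.2 has no outlier rule.

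**The concern.** The verdict is three confidence intervals set against fixed limits, so which values enter the model should be settled in advance. Four things are left open.

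1. **Whether a value beyond ± 3 SD must go or may go.** Step 2e and the introduction to the procedure differ.
2. **What justifies removal.** Distance alone suffices. In a device comparison, an extreme exposure may be the device effect itself. Protocol 2.2.4 reports exposure up to 62% higher with the AI than the PFS in the abdomen in an earlier study.
3. **Which dataset the test runs on.** It could be all participants, one device arm or one device-by-site cell, and the choice changes what is deleted.
4. **Whether the reader sees the all-data result.** It is promised for tiny datasets and within-profile data, but not for the comparison that decides the trial.

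The study is open-label, and the only stated approval of an exclusion is sign-off of the CSR. Nothing says the decision comes before the treatment comparison is seen.

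**Working it through.** **Inputs from the documents** (Protocol 9.5, SAP 7, SAP 9.3.2, Table AMBX.1): 108 per arm, CV 40%, expected ratio 1.07, limits 0.8 to 1.25, 90% CI, and a model with device, location and weight stratum. Cell sizes are 216/2 = 108 per arm, 108/3 = 36 per device-by-site cell and 36/3 = 12 per weight stratum within a cell. All are at least 6, so the n ≥ 6 branch applies at full enrolment.

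**Step 1: reproduce the stated power.**
- Log SD = sqrt(ln(1 + 0.40²)) = 0.3853.
- SE of the device difference = 0.3853 × sqrt(2/108) = 0.0524.
- Exact two one-sided tests power at a ratio of 1.07 = 90.5%, against the stated value of about 90%.

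**Step 2: the leverage of one value.** Removing one value 3 SD out moves the ratio by a factor of about exp(3 × 0.3853/108) = 1.011, or 1.1%.

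**Step 3: simulate the rule.** The simulation used 216 participants in the planned layout, the SAP model (210 df), and no true location or weight effect. The leave-one-out ± 3 SD test was iterated as written and applied automatically to one parameter. There were 60,000 log-normal trials at a true ratio of 1.25, 30,000 at 1.07, and 30,000 with t(4) errors of the same SD at 1.25. Monte Carlo SE for the bioequivalence (BE) rates is about 0.09 to 0.18 points.

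| | All data | Pooled | Per arm | Per cell |
|---|---|---|---|---|
| At least one valid value deleted, log-normal | – | 50% | 56% | 73% |
| False BE at 1.25, log-normal | 4.9% | 6.5% | 5.5% | 5.8% |
| Power at 1.07, log-normal | 90.9% | 92.2% | 91.0% | 90.9% |
| False BE at 1.25, t(4) tails (assumed) | 5.1% | 10.6% | 6.5% | 6.7% |

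Pooling is worst because, at a true ratio of 1.25, high AI values and low PFS values lie furthest from the common mean. Deleting them pulls the ratio towards 1, by a mean factor of 0.994 in a 6,000-trial log-normal run, against 1.000 per arm.

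**Step 4: the effect of leaving the choice open.** If the most favourable of the four versions is picked afterwards, false BE at 1.25 is 7.2%. At 1.07 the four versions do not all give the same verdict in 3.7% of trials.

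**Step 5: milder and joint cases.**
- If only values beyond 3.5 SD are ever suspected (assumption), deletion occurs in 12/15/29% of trials (pooled/arm/cell) and false BE is 5.2/5.0/5.1%.
- With all three parameters required and all ratios at 1.25 (assumed correlations 0.8 between Cmax and AUC, 0.99 between the AUCs; 20,000 trials), false BE is 2.4% with all data and 3.3/2.8/2.8% pruned. The single-parameter figures are the relevant bound when only one parameter is at its limit.

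**Step 6: an illustration with aberrant device exposures (assumption).** Suppose 5% of AI participants have exposure about 5-fold high (+1.6 log units) and the ratio is 1.07 otherwise. BE is then declared in 35% of 3,000 trials with all data and 83% after per-arm deletion. The overall geometric ratio is 1.07 × exp(0.05 × 1.6) = 1.16, inside the limits. This is therefore not a false-positive rate; it shows how far the verdict can depend on the deletion.

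**The case against.** The strongest reply is that the introduction governs. The procedure is optional, concerns potential exclusion, and is entered only for a value someone already finds atypical, so step 2e merely says what qualifies. The rule also sits with parameter derivation in 9.3.1, while the model in 9.3.2 never invokes it. Complete profiles are protected. Exclusions are documented and data are listed, so the all-data result could be rebuilt. The criterion is numerical and written into a SAP to be signed before the first participant visit.

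On size, BE needs all three parameters. The joint error stays below 5% even with t(4) tails shared across parameters: 2.2% with all data and 4.8/2.7/2.5% pruned (pooled/arm/cell; 8,000 trials, same assumed correlations, all ratios 1.25). No document supports heavy tails, and the plan describes no step that picks the best of four versions.

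Much of this stands. Automatic deletion is an upper case, the effect is small under log-normality, and use on the primary model is left open rather than stated. The protocol expects the SAP to add technical detail, so the absence of an outlier rule there is not a contradiction.

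The reply does not close the gap. Discretion with no required cause is what leaves the choice until after the data are seen. Protecting complete profiles does not protect a single Cmax or AUC value. A result the reader must rebuild from listings is not a planned analysis.

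**Conclusion.** The concern holds. The SAP permits, and in step 2e words as mandatory, the deletion of values with no assignable cause. The primary model is not exempted, the test dataset is not named, and no all-data result is promised at the planned sample size.

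Under the plan's assumptions the cost is modest: for one parameter at the limit, 0.6 to 1.6 points of extra false BE with automatic use, and 2.3 points if the version is chosen afterwards (7.2% against 4.9%). It grows to 1.4 to 5.5 points only under assumed t(4) tails, and is smaller when all three parameters sit at the limit. This should be fixed because it leaves an avoidable post-data choice in an open-label BE verdict and the remedy is cheap. It does not show that the planned conclusion would be wrong.

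**What to change.** - In SAP 9.3.2, state that the primary model uses every evaluable value in the PK population, except values with a documented assay, sampling or dosing error identified before treatment comparisons are seen.
- Keep the ± 3 SD test only to flag values, and name the dataset it runs on.
- Report any analysis that leaves out flagged values as a sensitivity analysis beside the all-data result, as the SAP already does for n < 6.
- Reword step 2e so that it agrees with the introduction to the procedure.

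The cost is SAP wording and one sensitivity table. The primary interval is slightly wider: mean log half-width 0.0865 with all data against 0.0851 after per-arm pruning (log-normal, ratio 1.07, 40,000 trials). The trade-off is that an extreme value which is really an error, but has no documented cause, stays in the primary interval.

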### Reporting of Excluded Values

Individual values excluded as outliers will be documented in the final CSR. Approval of the final CSR will connote approval of the exclusion.

#### **9.3.2 Pharmacokinetic Statistical Methodology**

The  $C_{\max}$ ,  $\text{AUC}(0-\infty)$ , and  $\text{AUC}(0-t_{\text{last}})$  will be log-transformed and analyzed using a linear fixed-effects model. The model will include delivery device, injection location, and weight

stratification as fixed-effects. The dosing regimen differences between the AI (Test) and PFS (Reference) administrations will be back-transformed to present the ratios of geometric least squares means and the corresponding 90% CI.

Example SAS Code:

```
proc mixed data=xxx;
by parameter;
class device location strat_weight;
model log_pk = device location strat_weight / residual;
lsmeans device / alpha=0.1 cl pdiff;
ods output lsmeans=lsmeans diffs=diffs;
run;
```

The  $t_{max}$  of mirikizumab between the AI (Test) and PFS (Reference) administrations will be analyzed using a Wilcoxon rank sum test. Estimates of the median difference, 90% CIs, and p-values from the Wilcoxon rank sum test will be calculated.

Additional comparisons will be made between:

- The 2 delivery devices (AI [Test] versus PFS [Reference]) separately at each injection location (injection location will be removed from the model above)
- The 3 injection locations (arm [Test] versus abdomen [Reference] and thigh [Test] versus abdomen [Reference]) separately for each device (device will be removed from the model above)

The 2 delivery devices (AI [Test] versus PFS [Reference]) will be considered bioequivalent if the 90% CIs of the ratio of geometric least squares means of  $C_{max}$ ,  $AUC(0-\infty)$ , and  $AUC(0-t_{last})$  fall within 0.8 to 1.25. CCI

Additional PK analyses may be conducted if deemed appropriate.

